9.1 Randomization

Donor livers will be randomly assigned to NMP or SCS with 1:1 allocation as per a computer generated randomization schedule using variable block randomization using the following stratification factors: participating (recipient) center and donor type (DBD or DCD). The randomization schedule will be created by the study statistician, and will remain confidential.

Allocation concealment will be ensured by use of central computerized randomization. Allocation will not be revealed until the recipient has been recruited to the trial and donor and recipient inclusion/exclusion criteria have been recorded. Random permuted block length will be used; block sizes will not be disclosed.

Prior to randomization, the local Investigator will confirm the availability of the investigational metra @ device. Once informed consent has been verified from the potential recipient of an organ and recipient and donor inclusion and exclusion criteria has been confirmed, the local recipient investigative site staff will proceed with randomization. Recipients will be considered enrolled in the study once a randomized liver has been assigned and there is an attempt to transplant the randomized liver. An attempt to transplant a liver is considered when there is knife-to-skin contact in the operating room during the recipient transplant procedure. A subject is considered to be transplanted when there is reperfusion of the donor liver in the recipient subject.

9.2 Re-Randomization

Because there is the potential for a donor liver to be randomized and the intended recipient to not receive the liver, the randomization schedule has been built such that the randomization assignment is unique to a donor liver, not a recipient. That is, if the intended recipient is unable to receive the liver and a new recipient is identified, the randomization assignment that was initially assigned remains, even if the new recipient is at a different site than the initial recipient.

It is also possible that a donor could be identified as one type (either DBD or DCD), and then switch to the other type after randomization has occurred. As in the previously mentioned scenario, the initial randomization assignment will be kept and it will be documented that the initial donor type has switched. See Section 11.5 for specific analysis plans in these instances.

9.3 Blinding

While it is not possible to blind the local Investigators to the method of organ preservation, Histopathologists at the central laboratory interpreting the biopsy specimens will remain blinded to the randomization group to the extent possible.

10. Sample Size Considerations

Power calculations of the superiority of NMP versus SCS were based on a test of inequality for two proportions using a pooled Z-test and one-sided α =0.025.

The following assumptions were considered:

EAD_{NMP}=10%

EAD_{SCS}=25%

Based on the above assumptions, it is estimated that 266 (approximately 356 total sample size considering approximately 25% attrition) transplanted livers will provide 90% overall power. Power calculations were conducted using PASS 14. Power for the primary analysis based on logistic regression is similar to this, and stratification based on sites will provide additional power if site is prognostic.

11. Data Structure and Handling

11.1 Data Handling and Transfer

Data management will be undertaken by NAMSA. NAMSA Biostatistics will be provided access to download SAS datasets or will be provided them upon request.

Programming of analysis datasets, tables, figures, and listings will be conducted during the data management phase of the study. Tables, figures, and listings may be reviewed prior to final data lock for data review. Any data values requiring investigation or correction will be identified, and protocol deviations will be reviewed. The final run of outputs will take place after the data are deemed final.

11.2 Missing Data

Endpoints may be missing because results of any of the 3 components of the EAD score are not analyzable, or because subjects have died, refused follow-up, or have withdrawn from the study. Section 12.5.1.3 outlines additional clinical decision techniques that will be used for those enrolled recipients where the endpoint is missing. If EAD is still unable to be determined after using these techniques, imputation methods will be used. Analyses that include imputation for missing data, are considered the standard analyses and will be used to analyze the primary endpoint.

Every effort will be made to obtain information regarding EAD for all recipients. If unavailable, the sponsor will report the reason for recipients with missing endpoint data. If the recipient is missing data and EAD cannot be determined using the additional clinically justified decision rules, the EAD endpoint will be imputed using baseline characteristics (i.e. treatment group, center, and donor type (DCD/DBD) as well as all available components of EAD collected during study follow-up (bilirubin, INR, and ALT/AST). This will be based on multiple imputation via full conditional specification imputation with the variables listed as above with logistic regression (and the endpoint listed last). Individual covariates may be omitted to still allow for

Ver 4.0 09SEP2020

imputation of the endpoint for the full randomized cohort if there are fitting issues with the covariate imputation process. An augmented likelihood approach will be used if there are fitting issues due to the separation or quasi-separation of data points. Imputation will be performed for 100 data sets. In line with multiple imputation, imputed data sets will be appropriately combined to produce a single estimate of treatment effect, along with the associated p-value for the hypothesis test.

Additional sensitivity analyses could include "completers only", last observation carried forward, and/or mixed models.

11.3 Visit Windows

The following outlines the scheduled visits post-transplant and the eligibility window:

Visit	Timing (from end of transplant procedure)
Day 1	12-24 hours
Day 2	24-48 hours
Day 3	48-72 hours
Day 4	72-96 hours
Day 5	96-120 hours
Day 6	120-144 hours
Day 7	144-168 hours
Day 10	216-288 hours
Day 30	$30 \text{ days} \pm 7 \text{ days}$
Month 3	3 months \pm 14 days
Month 6	6 months \pm 14 days
Month 12	12 months \pm 30 days

11.4 Pooling of Data

11.4.1 Across Trial Sites

Up to 15 sites will enroll recipients in the study. Statistical investigation of the homogeneity of results across investigational sites will be performed in order to ensure the poolability of results to address the primary endpoint. Statistical analyses used to assess the site by treatment interaction will be tested at a significance level of p=0.10.

11.4.2 Across Donor Types

Livers received from both DBD and DCD donors will be included in this study. Statistical investigation of the homogeneity of results across donor type will be performed in order to

ensure the poolability of results to address the primary endpoint. Statistical analyses used to assess the donor type by treatment interaction will be tested at a significance level of p=0.10.

11.5 Sensitivity Analysis

As mentioned in section 9.2, there may be instances where a donor type was reported as either DBD or DCD prior to randomization and then after the randomization is assigned, the donor type converts. Also, there may be a scenario where a liver is randomized within a stratification factor that is not actually appropriate for the liver (i.e., randomized in the DBD arm but actually a DCD liver). In both of these instances, subjects will be analyzed for the primary analysis in the original donor type group that the randomization assignment was based on. As a sensitivity analysis, those that switched donor types will be analyzed in the donor type group that they switched to, or those that were inappropriately randomized in the wrong stratification group will be analyzed in the correct donor type group, and the analysis will be re-run. If there is no significant impact on the results, subjects will be analyzed according to their original donor type group for all relevant analyses. A similar approach will be taken to investigate the impact of those donor livers that were randomized to the NMP arm, and needed to be converted to SCS at some point during the transport process. Additionally, sensitivity analyses will be conducted to demonstrate the impact on primary endpoint results using multiple imputation for EAD status that is unable to be confirmed by complete labs or at least 1 lab value meeting criteria for EAD.

12. Statistical Analyses

12.1 General Considerations

Continuous measures will be summarized with sample size, mean, median, standard deviation, minimum, and maximum; categorical measures will be presented with the counts and percentages of subjects in each category. Exact 95% binomial confidence intervals will also be computed and presented for binomial variables; such as EAD.

The date of attempted transplant will be considered study day 1.

Both DRI and MELD scores will be calculated outside of the database using the following calculations:

Donor risk index (DRI) = $\exp[(0.154 \text{ if } 40 \le \text{age} < 50) + (0.274 \text{ if } 50 \le \text{age} < 60) + (0.424 \text{ if } 60 \le \text{age} < 70) + (0.501 \text{ if } 70 \le \text{age}) + (0.079 \text{ if } \text{COD} = \text{anoxia}) + (0.145 \text{ if } \text{COD} = \text{CVA}) + (0.184 \text{ if } \text{COD} = \text{other}) + (0.176 \text{ if } \text{race} = \text{African American}) + (0.126 \text{ if } \text{race} = \text{other}) + (0.411 \text{ if } \text{DCD}) + (0.422 \text{ if } \text{partial/split}) + (0.066 ((170-\text{height})/10)) + (0.105 \text{ if } \text{regional share}) + (0.244 \text{ if } \text{national share}) + (0.010 \times \text{cold time})]. (Feng, 2006)$

Given the data collected in the OrganOx study, the following gives specific detail on fields collected and how they are used to calculate DRI:

Field in database Cause of death:	Parameter in Feng,2006 calculation	
Cause of death. CVA	CVA	
Anoxia	Anoxia	
Ver 4.0 09SEP2020	CONFIDENTIAL	Page 9 of 18

Hypoxia Trauma Other	Anoxia reference Other
Other	Other
Race:	
American Indian or Alaska Native	Other
Asian	Other
Black or African American	African American
Native Hawaiian or other Pacific Islander	Other
White	reference
Other	Other
Partial/Split	excluded from study
Location	
Local	reference
Regional	Regional
National	National
Cold time	all livers will be assumed to have a stored cold time Of 8 hours (which is the reference), thus no coefficient will be included for cold time.

MELD Score = 0.957 x Loge(creatinine mg/dL) + 0.378 x Loge(bilirubin mg/dL) + 1.120 x Loge(INR) + 0.643

The MELD score is then multiplied by 10 and rounded to the nearest whole number. Any lab values that are less than 1 are set to 1 one for the purpose of the calculation, and the maximum serum creatinine considered is 4.0 (values over 4.0 are set to 4.0). If a recipient had dialysis twice in the week prior to the serum creatinine test or received 24 hours of continuous venovenous hemodialysis (CVVHD) within the prior 7 days, the serum creatinine value is also set to 4.0 for the purposes of the calculation (https://www.unos.org/wp-content/uploads/unos/MELD_PELD_Calculator_Documentation.pdf).

The maximum MELD score is 40. For recipients with an initial MELD score greater than 11, then MELD score is then re-calculated as follows:

MELD Score = MELD(i) + 1.32*(137-Na) - (0.033*MELD(i)*(137-Na))

Sodium values less than 125 mmol/L will be set to 125, and values greater than 137 mmol/L will be set to 137. (see Appendix)

12.2 Analysis Populations

The primary endpoint will be analyzed among all transplanted subjects.

12.3 Subject Disposition

Subject disposition will be presented by:

- Summary of subjects (completed and expected) per office visit and completed outcome data from obtained medical records.
- Summary of discontinuation in the study and reason for discontinuation.

12.4 Demographics and Baseline Characteristics

Demographics and baseline characteristics of enrolled subjects will be summarized. These factors will include (but not be limited to):

- Age
- Gender
- Ethnicity
- Race

12.5 Primary Analysis

12.5.1 Primary Objective

The primary objective of this study is to compare the effect of NMP to SCS in the prevention of preservation injury and graft dysfunction, as measured by early allograft dysfunction (EAD).

12.5.1.1 Endpoint Definition

The primary endpoint in this study is the severity of immediate graft injury as measured by EAD in the NMP group as compared to SCS.

12.5.1.2 Hypothesis and/or parameters to be estimated

The primary endpoint analysis will be performed on all transplanted subjects. The objective of the primary analysis is to show EAD in the NMP cohort less than the observed EAD rate from the SCS cohort. The hypothesis can be written as follows:

 $\begin{array}{l} H_0: \ EAD_{NMP} \geq EAD_{SCS} \\ H_A: \ EAD_{NMP} < EAD_{SCS}, \\ \ \text{where EAD is a binary outcome defined by the presence of one of the following 3 outcomes} \\ [1]: \end{array}$

- 1. Serum bilirubin $\geq 10 \text{ mg/dL}$ at day 7 post-transplant
- 2. International normalized ratio \geq 1.6 at day 7 post-transplant
- 3. ALT or AST > 2000 IU/L within the first 7 days post-transplant

12.5.1.3 Data Collection and Analysis Methods

Serum bilirubin at day 7 post-transplant, International normalized ratio at day 7 post-transplant, and ALT or AST within the first 7 days post-transplant (collectively "Lab Values") are all reported on the Inpatient Stay (Day 1 through Day 10 Follow-up) CRF. In the event that a recipient is missing information for the endpoint, the following techniques will be employed to impute the primary endpoint outcome for the recipient:

- a. If day 7 INR is missing and day 6 is available, the day 6 value will be used.
- b. If a recipient has been discharged from hospital prior to day 7 post-transplant and the recipient had complete Lab Values before discharge that did not meet the definition of EAD, the recipient will be considered to not have an EAD event.
- c. If the last INR value recorded for a recipient is less than the threshold for EAD and the recipient has complete Lab Values for all other components of EAD that do not meet the definition of EAD, the recipient will be considered to not have an EAD event. Available follow-up Lab Values must also be below the threshold and no readmissions reported to be considered to not have an EAD event.

The primary analysis will be a logistic model, adjusted for participating (recipient) center using SAS proc logistic or a similar procedure. Significance for the treatment effect will be assessed by the p-value associated with the treatment group assignment.

12.6 Secondary Endpoints

All secondary endpoints will be assessed for all transplanted subjects with analyzable results. No formal statistical hypothesis testing will be performed.

During preparation of the 30-day clinical study report, it was discovered that the outcome measures for secondary endpoints #6 and #7 were inadvertently switched during preparation of the study protocol; therefore, the correct outcome measures for these endpoints have been updated and are reported below.

12.6.1 Secondary Objective #1

To compare graft and subject survival between NMP and SCS livers.

12.6.1.1 Endpoint Definition

The following compose the secondary objective #1: 1) Primary non-function rates: irreversible graft dysfunction requiring emergency liver replacement during the first 10 days after liver transplantation; 2) Graft survival rates at 30 days, 3 months, and 6 months following transplantation; and 3) Subject survival rates at 30 days, 3 months, and 6 months following transplantation.

12.6.1.2 Hypothesis and/or parameters to be estimated

No formal statistical hypothesis testing will be performed for the secondary endpoint. Primary non-function, graft survival, and subject survival will be reported.

12.6.1.3 Data Collection and Analysis Methods

The time of knife-to-skin contact (used as study day 0) is collected on either the Transplant Operation NMP or Transplant Operation SCS CRF. Primary Graft Non-Function (Yes/No) is reported on the Inpatient Stay (Day 1 through Day 10 Follow-up) CRF as well as the date of primary graft non-function. The day 30, 3 month, and 6 month follow-up assessment forms have information regarding graft survival (yes/no) and graft failure dates, and the Adverse Event. The end of study CRFs report whether or not a subject is deceased.

The incidence of primary non-function rates will be measured, as well as the Kaplan-Meier rate and corresponding 95% confidence interval based on Greenwood's formula for both graft survival and subject survival.

12.6.2 Secondary Objective #2

To compare evidence of post-reperfusion syndrome between NMP and SCS livers on transplantation.

12.6.2.1 Endpoint Definition

Secondary endpoint #2 is the assessment of mean arterial pressure (MAP) pre- and post-reperfusion and requirement for vasopressor use.

12.6.2.2 Hypothesis and/or parameters to be estimated

No formal statistical hypothesis testing will be performed for the secondary endpoint. Occurrence of post-reperfusion syndrome and use of vasopressors will be reported within each treatment arm.

12.6.2.3 Data Collection and Analysis Methods

Both occurrence of post-reperfusion syndrome and use of vasopressors will be collected and reported on the Transplant Operation NMP and Transplant Operation SCS CRF.

The incidence of post-reperfusion syndrome and use of vasopressors will be measured. Post-reperfusion syndrome is defined as a decrease in mean arterial pressure (MAP) of more than 30% from the baseline value for more than one minute during the first five minutes after reperfusion.

12.6.3 Secondary Objective #3

To compare biochemical liver function between NMP and SCS livers.

12.6.3.1 Endpoint Definition

The components of secondary endpoint #3 are: 1) Bilirubin, GGT, ALT, AST, ALP, and INR at days 1-7, day 30, month 3, and month 6 post-transplant.; and 2) Lactate at days 1-7 while the subject is in ICU.

Ver 4.0 09SEP2020

12.6.3.2 Hypothesis and/or parameters to be estimated

No formal statistical hypothesis testing will be performed for the secondary endpoint. Statistics for Bilirubin, GGT, ALT, AST, ALP, and INR at the different time points will be summarized, as well as lactate.

12.6.3.3 Data Collection and Analysis Methods

All variables of interest will be collected and reported on in the Inpatient Stay (Day 1 through Day 10 – Follow-up) CRF. In addition, Bilirubin, GGT, ALT, AST, ALP, and INR are also reported on the 30 Day Follow-up, 3 Month Follow-Up, and 6 Month Follow-Up CRFs.

The mean, median, min, max, and interquartile range (IQR) will be summarized for all variables at all appropriate time points.

Data that are not required will be reported for those subjects with data available.

12.6.4 Secondary Objective #4

To compare evidence of ischemia-reperfusion injury between NMP and SCS livers.

12.6.4.1 Endpoint Definition

Post-reperfusion biopsies will be compared to baseline pre-reperfusion biopsies and graded according to standard histological criteria.

12.6.4.2 Hypothesis and/or parameters to be estimated

No formal statistical hypothesis testing will be performed for the secondary endpoint, however evidence of ischemia reperfusion injury between NMP and SCS livers will be reported.

12.6.4.3 Data Collection and Analysis Methods

Post-reperfusion biopsies will be compared to baseline pre-reperfusion biopsies and graded according to standard histological criteria and collected on the Core Lab CRF.

12.6.5 Secondary Objective #5

To compare evidence of biliary complications between NMP and SCS livers.

12.6.5.1 Endpoint Definition

Incidence of biliary investigations and/or interventions between 7 days and 6 months post-transplant.

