6.4.4 BLINDING/MASKING

While it is not possible to blind the local Investigators to the method of organ preservation, Histopathologists at the central laboratory interpreting the biopsy specimens will remain blinded to the randomization group to the extent possible.

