6.7 CONCOMITANT CARE

All other aspects of the retrieval procedure will be carried out according to local policies and national guidelines.

Recipient management including the transplantation procedure, postoperative care, immunosuppression and other medications, and post-transplant monitoring will follow local protocols.

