6.8.4.3 SAFETY ASSESSMENTS

The following safety data will be collected and recorded:

- 1. Recipient infection (documented positive microbiological culture, pathological lesion, or clinical criteria met)
- 2. Biopsy-proven acute rejection episodes
- 3. Biliary investigations (MRCP, ERCP, PTC)
- 4. Biliary interventions (surgical, radiological, or endoscopic)
- 5. Hepatic vascular complications (e.g., hepatic artery stenosis, hepatic artery thrombosis, portal vein thrombosis, portal vein stenosis)
- 6. Reoperation for graft related complications
- 7. Adverse event(s)

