12.6.5.2 Hypothesis and/or parameters to be estimated

No formal statistical hypothesis testing will be performed for the secondary endpoint; however, incidence of biliary investigations and/or interventions will be reported.

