12.6.5.3 Data Collection and Analysis Methods

Date of knife-to-skin contact is available on either the Transplant Operation NMP or Transplant Operation SCS CRF. The 'Action Taken' and 'If biliary investigation checked: Was there a biliary intervention' on the Adverse Event CRF as well as the Date of onset of the event are used to calculate time to event

The Kaplan-Meier rate and corresponding 95% confidence interval based on Greenwood's formula will be reported at 7-days, 30-days, 3-months, and 6-months post-transplant.

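### The biliary endpoint pools tests with treatments, so the planned output cannot show whether a difference between arms reflects complications or the ordering of tests by unblinded teams

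*SAP*

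**What the plan says.** Secondary Objective #5 is to compare evidence of biliary complications between the arms. SAP 12.6.5.1 defines the endpoint as "Incidence of biliary investigations and/or interventions between 7 days and 6 months post-transplant"; the protocol synopsis and the outcome table in Protocol 3.2.2 have the same definition. SAP 12.6.5.2 rules out formal testing and says that "incidence of biliary investigations and/or interventions will be reported".

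For data, SAP 12.6.5.3 names "The 'Action Taken' and 'If biliary investigation checked: Was there a biliary intervention' on the Adverse Event CRF", together with the onset date of the event. It plans Kaplan-Meier rates with 95% Greenwood intervals at 7 days, 30 days, 3 months and 6 months.

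The Protocol's safety assessments (6.8.1.3, 6.8.2.3, 6.8.3.3, 6.8.4.3) list biliary investigations (MRCP, ERCP, PTC) and biliary interventions (surgical, radiological or endoscopic) as two separate items. Neither item requires a positive finding.

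On who orders the tests, Protocol 6.7 says: "Recipient management including the transplantation procedure, postoperative care, immunosuppression and other medications, and post-transplant monitoring will follow local protocols". Protocol 6.4.4 says that "it is not possible to blind the local Investigators to the method of organ preservation". The schedule in Appendix A1 contains no biliary imaging and no trigger for it.

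**The concern.** Within the composite, a negative MRCP ordered for raised liver enzymes and a treated complication each count as one event. The first depends heavily on the clinician's threshold for looking. That threshold is set locally, by a team that knows how the liver was stored. Stratifying randomization by center balances differences in imaging habits between centers. It does not balance decisions within a center that depend on knowing the arm.

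What is at stake is how the reported rates and intervals are read. If they differ, a reader cannot tell whether one arm had more biliary disease or was looked at more often. If they agree, a real difference in treated complications could still be hidden. The information that would separate these cases is collected, but SAP 12.6.5 plans no table that shows it.

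**Working it through.** **The plan's own figure.** The documents state no rate, effect size or power for the biliary endpoint. The only sample size is for EAD, and it is used here only to fix the number per arm. With 25% versus 10%, one-sided 0.025, 90% power and a pooled Z-test, n = [1.960 × √(2 × 0.175 × 0.825) + 1.2816 × √(0.25 × 0.75 + 0.10 × 0.90)]² / 0.15² = 132.8. That rounds up to 133 per arm, or 266 in total, as stated in Protocol 9.2 and SAP 10.

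**How an investigation becomes an event.**
- SAP 12.6.5.3 takes events from the Adverse Event CRF, so a test with no linked adverse event may not count.
- Protocol 8.2.1 includes abnormal laboratory findings among adverse events, and 8.2.5 has the local investigator record them. A test ordered for abnormal enzymes can therefore enter with no biliary diagnosis.
- The field "If biliary investigation checked: Was there a biliary intervention" separates tests that led to treatment from those that did not. SAP 12.6.5.3 names it only as an input to time to event.
- SAP 12.9 and 12.10 add no separate intervention rate for transplanted recipients.

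**Illustration; all biliary rates are assumed and censoring is ignored.** Let c be the proportion with a treated complication and q the proportion of the remainder who are investigated without intervention. Then composite = c + (1 − c) × q.

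With c = 12% in both arms:
- q = 5%: 0.12 + 0.88 × 0.05 = 16.4%
- q = 10%: 0.12 + 0.88 × 0.10 = 20.8%
- q = 15%: 0.12 + 0.88 × 0.15 = 25.2%

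Against 5% in the other arm, the composite differs by 4.4 or 8.8 points although treated complications are identical.

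**Range.** When c is equal in both arms, the difference is (1 − c) × (gap in q). For c from 10% to 20%:
- 5-point gap: 4.0 to 4.5 points
- 10-point gap: 8.0 to 9.0 points
- 15-point gap: 12.0 to 13.5 points

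**Masking.** Suppose treated complications are 15% on SCS and 8% on NMP, with q = 10% on SCS and 20% on NMP. The composite is 0.15 + 0.85 × 0.10 = 23.5% on SCS and 0.08 + 0.92 × 0.20 = 26.4% on NMP, so the direction reverses.

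**Condition on the split.** An intervention-only rate equals c in each arm only if the decision to intervene, and the chance of finding something to treat, do not depend on arm.

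**The case against.** The strongest reply is that this is a prespecified, descriptive secondary endpoint, the same in protocol and SAP, and that investigations and interventions are a fair proxy for evidence of complications. Much of that stands. Trial success rests on EAD alone, and its type I error is untouched.

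Some stronger readings are tempting, and the documents do not support them:

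- *Every MRCP, ERCP or PTC counts.* Events enter through an adverse-event record. A Clinical Events Committee of non-participating clinicians also reviews and classifies adverse events (Protocol 1.8.2). The documents do not say that it is blinded or that it confirms biliary endpoint events, so this is only a partial safeguard.
- *This is the only biliary information in the trial.* The protocol lists interventions as a separate safety item, and 9.1.6 says safety data will be reported. Nor does the SAP forbid component rows. What is missing is a planned row that shows them by arm.
- *The objective cannot be answered.* The objective concerns evidence of complications, and the composite is some evidence.
- *There is a high false-positive risk.* A nominal two-sided 5% test of 16.4% against 25.2% would reject about 42% of the time, but the trial runs no such test and the rates are assumed.
- *Interventions alone are unbiased.* The same unblinded teams decide on them, and more looking may find more to treat.

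A change of emphasis late in an open-label trial is also a fair worry. SAP version 4.0 says enrollment was complete, and a 30-day report had already been in preparation.

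**Conclusion.** The point holds as a matter of reporting and interpretation. The planned composite cannot distinguish a difference in treated complications from a difference in testing, and testing is discretionary and unblinded. Under the assumptions shown, a 5- to 15-point gap in investigation without treatment moves the composite by 4.0 to 13.5 points when treated complications are equal. The documents establish neither that such a gap exists nor its direction.

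A reader might infer that interventions should replace the composite as the basis for conclusions. The documents do not support that: the composite is prespecified, and interventions share part of the same weakness. Showing the components beside it is a low-cost improvement, and nothing in the primary analysis depends on it.

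**What to change.** Keep the composite in SAP 12.6.5 unchanged. Add two rows by arm, over the same window and time points, with Kaplan-Meier rates and 95% intervals:

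1. biliary intervention (surgical, radiological or endoscopic);
2. biliary investigation without intervention.

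State how a recipient with both is classified; counting that recipient in row 1 only makes the two counts add up to the composite. The CRF intervention field is described as conditional on an investigation being checked, so confirm that an intervention recorded without that check is still captured.

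Add two sentences of interpretation. First, a composite difference driven by investigation-only events is not evidence of a difference in biliary complications. Second, interventions are also unblinded decisions, so the split reduces ascertainment bias without removing it. If the rows are added after data have been seen, label them as additional analyses under Protocol 9.3.

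The cost is SAP wording and two table rows, with no new data collection. Each component has fewer events than the composite, so its interval is wider relative to the rate. At the assumed 12%, row 1 would have about 16 recipients per arm (0.12 × 133).
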